12.1.1 Primary Efficacy Endpoint

The primary efficacy endpoint is the responder rate as identified by the OMERACT-OARSI responder index at 39 weeks post treatment comparing the Cingal group to the triamcinolone hexacetonide group

The response rate for the Cingal group and Triamcinolone Hexacetonide (TH) group will be calculated and tested using Fisher's exact test. Formally, the hypothesis to be tested is:

$$H_0: \pi_C = \pi_T \text{ versus } H_A: \pi_C \neq \pi_T$$

Where π_C is the responder rate for the Cingal group and π_T is the responder rate for the triamcinolone hexacetonide group.

12.1.2 Secondary Efficacy Endpoints

There are multiple secondary endpoints. In order to preserve the integrity of the Type I error, these will be tested in a hierarchical manner. The order of the testing is as the order presented here.

The change from baseline in knee pain as measured by the WOMAC Pain Score (100 mm VAS) at 39 weeks post treatment comparing the Cingal group to the TH group.

This secondary efficacy endpoint is the change from baseline in knee pain as measured by the WOMAC Pain Score (100 mm VAS) at 39 weeks post treatment comparing the Cingal group to the TH group.

Data will be analyzed via an analysis of variance (ANOVA) with a term for treatment and baseline pain score as a covariate. The primary hypothesis will be tested by a predefined contrast for comparing the Cingal group to the TH group. Formally, the hypothesis to be tested is:

$H_0: \mu_{DC} = \mu_{DT}$ versus $HA: \mu_{DC} \neq \mu_{DT}$.

Where μ_{DC} is the mean change from baseline in the WOMAC Pain Score for the Cingal group at 39 weeks and μ_{DT} is the mean change from baseline in the WOMAC Pain Score for the TH group at 39 weeks. Since there are three treatment groups in this study, this hypothesis will be tested using a one way ANOVA and constructing a contrast for this hypothesis. This process is the same as using a baseline pain adjusted two-sample t-test with the common variance estimate from the ANOVA.

The change from baseline in WOMAC Physical Function score at 39 weeks post treatment comparing the Cingal group to the triamcinolone hexacetonide group.

This secondary efficacy endpoint is the change from baseline in WOMAC Physical Function Score at 39 weeks post treatment comparing the Cingal group to the TH group.

Data will be analyzed via an analysis of variance (ANOVA) with a term for treatment and baseline Physical Function score as a covariate. The hypothesis will be tested by a predefined contrast for comparing the Cingal group to the TH group. Formally, the hypothesis to be tested is:

$H_0: \mu_{DC} = \mu_{DT}$ versus $HA: \mu_{DC} \neq \mu_{DT}$.

Where μ_{DC} is the mean change from baseline in the WOMAC Physical Function Score for the Cingal group at 39 weeks and μ_{DT} is the mean change from baseline in the WOMAC Physical Function Score for the TH group at 39 weeks.

The change from baseline in WOMAC Stiffness score at 39 weeks post treatment comparing the Cingal group to the triamcinolone hexacetonide group.

This secondary efficacy endpoint is the change from baseline in WOMAC Stiffness Score at 39 weeks post treatment comparing the Cingal group to the TH group.

Data will be analyzed via an analysis of variance (ANOVA) with a term for treatment and baseline Stiffness score as a covariate. The hypothesis will be tested by a predefined contrast for comparing the Cingal group to the TH group. Formally, the hypothesis to be tested is:

$H_0: \mu_{DC} = \mu_{DT}$ versus $H_A: \mu_{DC} \neq \mu_{DT}$.

Where μ_{DC} is the mean change from baseline in the WOMAC Stiffness Score for the Cingal group at 39 weeks and μ_{DT} is the mean change from baseline in the WOMAC Stiffness Score for the TH group at 39 weeks.

The change from baseline in Total WOMAC score at 39 weeks post treatment comparing the Cingal group to the triamcinolone hexacetonide group.

This secondary efficacy endpoint is the change from baseline in Total WOMAC Score at 39 weeks post treatment comparing the Cingal group to the TH group.

Data will be analyzed via an analysis of variance (ANOVA) with a term for treatment and baseline Total WOMAC score as a covariate. The hypothesis will be tested by a predefined contrast for comparing the Cingal group to the TH group. Formally, the hypothesis to be tested is:

$H_0: \mu_{DC} = \mu_{DT}$ versus $H_A: \mu_{DC} \neq \mu_{DT}$.

Where μ_{DC} is the mean change from baseline in the Total WOMAC Score for the Cingal group at 39 weeks and μ_{DT} is the mean change from baseline in the Total WOMAC Score for the TH group at 39 weeks.

The change from baseline in the Patient Global Assessment at 39 weeks post treatment comparing the Cingal group to the triamcinolone hexacetonide group.

Since this is a secondary endpoint the data will be analyzed for each time point individually with no adjustment for multiplicity. Data will be analyzed via an analysis of variance with a term for treatment and baseline pain score as a covariate. The primary hypothesis will be tested by a predefined contrast for comparing the Cingal group to the Triamcinolone Hexacetonide group. Formally, the hypothesis to be tested is:

$H_0: \mu_{DC} = \mu_{DT}$ versus $H_A: \mu_{DC} \neq \mu_{DT}$.

Where μ_{DC} is the mean change from baseline in the Patient Global Assessment Score for the Cingal group at 39 weeks and μ_{DT} is the mean change from baseline in the Patient Global Assessment Score for the triamcinolone hexacetonide group. At 39 weeks. Since there are three treatment groups in this study, this hypothesis will be tested using a one way ANOVA and constructing a contrast for this hypothesis. This process is the same as using a two-sample t-test with the common variance estimate

from the ANOVA.

The change from baseline in the Evaluator Global Assessment through 39 weeks post treatment comparing the Cingal group to the triamcinolone hexacetonide group.

Since this is a secondary endpoint the data will be analyzed for each time point individually with no adjustments for multiplicity. Data will be analyzed via an analysis of variance with a term for treatment and baseline pain score as a covariate. The primary hypothesis will be tested by a predefined contrast for comparing the Cingal group to the triamcinolone hexacetonide group. Formally, the hypothesis to be tested is:

$$H_0: \mu_{DC} = \mu_{DT} \text{ versus } H_A: \mu_{DC} \neq \mu_{DT}$$

Where μ_{DC} is the mean change from baseline in the Evaluator Global Assessment for the Cingal group at 39 weeks and μ_{DT} is the mean change from baseline in the Evaluator Global Assessment for the triamcinolone hexacetonide group at 39 weeks. Since there are three treatment groups in this study, this hypothesis will be tested using a one way ANOVA and constructing a contrast for this hypothesis. This process of constructing a contrast is the same as using a two-sample t-test with the common variance estimate from the ANOVA.

The usage of rescue medication through 39 weeks post treatment comparing the Cingal group to the triamcinolone hexacetonide group.

This secondary efficacy endpoint is the usage of rescue medications through 39 weeks post treatment comparing the Cingal group to the TH group.

The hypothesis will be tested by a predefined contrast for comparing the Cingal group to the TH group. Formally, the hypothesis to be tested is:

$$H_0: \mu_{DC} = \mu_{DT} \text{ versus } H_A: \mu_{DC} \neq \mu_{DT}.$$

Where μ_{DC} is the total usage of rescue medications for the Cingal group at 39 weeks and μ_{DT} is the mean change from baseline in the WOMAC Pain Score for the TH group at 39 weeks.

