2 DEFINITIONS

Baseline: The assessments performed prior to the study injection after the Screening Visit.

Blinded Evaluator: The Blinded Evaluator will be a physician, research nurse, registered physiotherapist or physician assistant trained by the PI to perform the assessments outlined in the protocol. The Blinded Evaluator will complete the physical evaluation of both knees, range of motion (ROM) assessment of both knees, and the Evaluator Global Assessment.

End of Study: End of study is defined as the last subject's last visit.

Enrolled: A subject who has signed the informed consent form (ICF) is enrolled.

Index Knee: The knee that meets the eligibility criteria for treatment. The index knee may also be termed the "study knee". In subjects with bilateral knee Osteoarthritis (OA), where both knees meet eligibility criteria, the more symptomatic knee is the index knee.

Ethics Committee (EC): EC refers to an independent body (e.g. Research Ethics Boards, Independent Ethics Committees) whose responsibility is to ensure the protection of rights, safety and well-being of human subjects involved in a trial. Committees with these responsibilities will be referred to in this document as Ethics Committees.

Rescue Medication: Acetaminophen/paracetamol will be distributed as the rescue medication. It is the only medication that should be taken for knee pain during the entire study. Rescue medication will be discontinued at least 48 hours prior to Baseline and all follow-up visits.

Treating Physician: The Treating Physician will most often be the Principal Investigator (PI). He/she will administer the Cingal®, Monovisc® or steroid injection but will not participate in the efficacy evaluation.

Treatment Failure: A subject who undergoes a procedure or uses a medication (other than the rescue medication) for the treatment of OA in the index knee at any time after the study injection through the 39 week visit.

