3 STUDY SYNOPSIS

Title	Extension Study to Cingal 16-02: Trial Extension to 39 Week Follow Up in the Randomized, Double-Blind, Active Comparator Controlled, Multi-Center Study of a Single Injection Cross-Linked Sodium Hyaluronate Combined with Triamcinolone Hexacetonide (Cingal) to Provide Symptomatic Relief of Osteoarthritis of the Knee
Study Objective	To evaluate the efficacy and safety of a single injection of Cingal for relief of joint pain at 39 week follow up in subjects with Osteoarthritis (OA) of the knee who have not responded to conservative treatment.
Investigational Product	Subjects enrolled in Cingal 17-02 will not receive an injection. For reference only, the investigational product utilized in Cingal 16-02 was: Cingal : A chemically cross-linked sodium hyaluronate supplied as a 4-mL unit dose with a nominal 18 mg of triamcinolone hexacetonide (TH) in a 5-mL glass syringe.
Comparator Product	Subjects enrolled in Cingal 17-02 will not receive an injection. For reference only, the comparator products utilized in Cingal 16-02 were: Triamcinolone Hexacetonide (TH) : 20 mg/ml supplied as 1 mL unit dose in a glass ampoule. Monovisc® : A chemically cross-linked sodium hyaluronate supplied as a 4-mL unit dose in a 5-mL glass syringe.
Mode of Delivery	For reference only, the mode of delivery in Cingal 16-02 was: Cingal, Triamcinolone Hexacetonide, or Monovisc will be injected into the intraarticular (IA) space of the index knee using an 18-21 gauge needle.
Study Design	Multi-center, randomized, double-blind, parallel group, 3-arm, active comparator controlled study
Phase	Phase III
Sample Size	A total of 576 subjects will be enrolled. This equates to 256 subjects injected with Cingal, 256 subjects injected with Monovisc and 64 subjects injected with TH. All subjects who meet enrollment criteria and completed the 26 week follow up in Cingal 16-02 will have the option to participate in the sub-study.
Study Duration	The entire sub-study duration will be an additional 13 weeks. The follow up visit will be scheduled at 39 weeks post treatment.

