7.2 Secondary Efficacy Endpoints

- The change from baseline in knee pain as measured by the WOMAC Pain Score (100 mm VAS) at 39 weeks post treatment comparing the Cingal group to the TH group.
- The change from baseline in WOMAC Physical Function score at 39 weeks post treatment comparing the Cingal group to the TH group.
- The change from baseline in WOMAC Stiffness score at 39 weeks post treatment comparing the Cingal group to the TH group.
- The change from baseline in Total WOMAC score at 39 weeks post treatment comparing the Cingal group to the TH group.
- The change from baseline in the Patient Global Assessment 39 weeks post treatment in the Cingal group compared to the TH group.
- The change from baseline in the Evaluator Global Assessment at 39 weeks post treatment in the Cingal group compared to the TH group.
- The usage of rescue medication through 39 weeks post treatment in the Cingal group compared to the TH group.

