8 STUDY DESIGN

8.1 Diagram

8.2 Trial Design

This sub-study is an extension of the ongoing Cingal 16-02 trial which is a multi-center, randomized, double-blind, parallel group, active comparator controlled trial to evaluate the efficacy and safety of a single injection of Cingal for the relief of joint pain in subjects with OA of the knee.

Subjects with OA defined as Kellgren-Lawrence (K-L) I-III in the index knee were eligible for this study [9, 10]. Felson et al 2004, encouraged the use of both OA symptoms and radiographic changes in the assessment of OA [11]. Cingal 16-02 study employed both methods to screen subjects. Structural severity was evaluated with the K-L classification score, a composite index of the presence and severity of joint space narrowing, osteophytes, sclerosis, deformity and cysts (see Appendix 4) [9, 10].

For the evaluation of symptomatic severity, two main domains are important [12]. The first is pain and the second is functional impairment. Other domains often used include subject's overall assessment, ROM and performance. Domains identified by OMERACT as core variables to be used in clinical trials involving OA are pain, function and the Patient Global Assessment which were captured as part of the Cingal 16-02 study [12].

Baseline and post-treatment pain, physical function and stiffness is measured using the WOMAC questionnaire in the Cingal 16-02 up to 26 weeks and then to 39 weeks within the Cingal 17-02 trial. Range of Motion, Patient and Evaluator Global Assessment and the EuroQol are used to assess symptomatic severity throughout both studies. In addition, the number of acetaminophen/paracetamol pills taken is captured as an indirect measure of pain and will be done at each visit.

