10.2 Procedure Description

10.2.1 Informed Consent Form (ICF)

The subject will be asked to sign the ICF prior to attending the 39 week follow up visit.

All data collected in the clinical trial Cingal 16-02 will be utilized in Cingal 17-02. The demographics and assessments conducted at screening and baseline for Cingal 16-02 will be utilized as the demographic and baseline data for Cingal 17-02.

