10.2.12.2 Rescue Medications

Acetaminophen/paracetamol (up to a maximum of 4.0 grams per day per the package insert or as per regional limitations) will be allowed as the rescue medication for the treatment of joint pain for the duration of Cingal 17-02. At least forty eight hours prior to the 39 week follow-up visit the subject should discontinue use of the rescue medication.

At the Screening Visit for Cingal 17-02, the rescue acetaminophen/paracetamol specifically labelled for use within Cingal 17-02 will be dispensed. The rescue medications provided to the subject for Cingal 16-02 should be returned to the investigational site at the Cingal 16-02 26 week follow up visit.

The subject should be instructed to bring the rescue medication with them to 39-week follow-up visit for a pill count. Additional rescue acetaminophen/paracetamol will be dispensed as needed only if there is an unscheduled the follow-up visit before the 39 week follow up visit.

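### The rescue-medication hypothesis sets total rescue use in the Cingal group against change in WOMAC pain in the TH group; both terms should be mean rescue use per day covered.

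*Protocol*

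**What the plan says.** Protocol 7.2 lists the endpoint as "The usage of rescue medication through 39 weeks post treatment in the Cingal group compared to the TH group", and SAP 3.2 lists the same comparison. It comes last of the seven secondary endpoints, which Protocol 12.1.2 and SAP 4.1.3 test in a fixed order.

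The hypothesis in those two sections is μ_DC = μ_DT against a two-sided alternative. The Cingal parameter "is the total usage of rescue medications for the Cingal group at 39 weeks". The TH parameter "is the mean change from baseline in the WOMAC Pain Score for the TH group at 39 weeks". The SAP repeats the protocol's wording for both. The test is a Cingal–TH contrast, with no model, unit, covariate or term for observation time.

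On collection, Protocol 8.2 says that "the number of acetaminophen/paracetamol pills taken is captured as an indirect measure of pain and will be done at each visit". Weeks 26 to 39 belong to the extension: subjects who meet the enrollment criteria and "completed the 26 week follow up in Cingal 16-02 will have the option to participate in the sub-study" (synopsis). Consent is separate: "The subject will be asked to sign the ICF prior to attending the 39 week follow up visit" (Protocol 10.2.1). Rescue supplies from the parent trial "should be returned to the investigational site at the Cingal 16-02 26 week follow up visit" (Protocol 10.2.12.2), and new stock is dispensed at the extension's screening visit.

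**The concern.** Read literally, the null compares two different variables in different units, so rejecting or retaining it says nothing about rescue use. The Cingal term is also a total, not a mean per subject. The protocol describes its methods section as the basis for the SAP, and the SAP carried the error over unchanged, so no later text puts it right.

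Replacing the TH term with total rescue use would leave a second, smaller weakness. Someone who does not join the extension has no planned rescue collection after week 26. Lower rescue use reads as benefit, so if totals cut off at week 26 were analysed and more subjects left one arm than the other, the arm with more leavers would look better with no true difference.

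**Working it through.** **1. The definitions side by side.**

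| Place | Cingal term | TH term |
|---|---|---|
| Protocol 7.2, SAP 3.2 (endpoint lists) | rescue use through week 39 | rescue use through week 39 |
| Protocol 12.1.2, SAP 4.1.3 (heading and first sentence) | rescue use through week 39 | rescue use through week 39 |
| Protocol 12.1.2, SAP 4.1.3 (hypothesis) | total rescue use | mean change in WOMAC pain |

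Only the TH term of the hypothesis is out of line. Its wording matches the definition used for the WOMAC pain endpoint at the start of the same section, which points to a carry-over. The exploratory text (Protocol 12.1.3, SAP 4.1.4) does not repair it: that measure is pills between visits, compared descriptively.

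**2. Size of the truncation effect.** The plan gives no figure for this endpoint, so there is none to reproduce. Inputs from the documents are 26 and 39 weeks, group sizes of 256, 256 and 64, and an expected missing rate below 1% (Protocol 12.5). Leaving rates by arm are not given; those below are assumptions.

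With constant daily use equal in both arms, leaving at week 26 unrelated to use, and a proportion p leaving, the mean raw total relative to full follow-up is 1 − p(1 − f), where f = 26/39 = 0.667.

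| Leaving, Cingal vs TH | Cingal | TH | TH lower by |
|---|---|---|---|
| equal | same | same | 0% |
| 0% vs 1% | 1 | 0.9967 | 0.3% |
| 5% vs 15% | 0.9833 | 0.9500 | 3.4% |
| 5% vs 20% | 0.9833 | 0.9333 | 5.1% |

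**3. Effect on the test.** This was simulated with gamma-distributed daily use (mean 1), leaving in Monovisc as in Cingal, the pooled-variance Cingal–TH contrast from a three-arm ANOVA, a two-sided 5% level and 40,000 trials (Monte Carlo standard error about 0.1 point). The coefficient of variation (CV) of daily use is an assumption. So is the ANOVA, because neither document names a model for this endpoint. Type I error:

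| Measure and leaving | CV 0.5 | CV 1.0 | CV 1.5 |
|---|---|---|---|
| Raw total, 5% vs 5% | 4.99% | 4.81% | 4.90% |
| Raw total, 0% vs 1% | 5.00% | 4.84% | 4.81% |
| Raw total, 5% vs 15% | 7.42% | 5.10% | 4.50% |
| Raw total, 5% vs 20% | 11.01% | 5.56% | 4.87% |
| Per observed day, 5% vs 15% | 5.05% | 4.86% | 4.93% |
| Extension signers only, 5% vs 15% | 4.77% | 4.86% | 4.85% |

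A two-sample pooled t-test on raw totals at 5% versus 15% gives 7.41%, 5.12% and 4.46%, so the assumed model hardly matters.

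**4. If daily use rises after week 26.** Take 1 per day to week 26 and 1.5 per day after it, in week-equivalents. A full total is 26 + 13 × 1.5 = 45.5; a leaver's total is 26. At 5% versus 15% leaving:

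- Raw total: 0.95 × 45.5 + 0.05 × 26 = 44.525 against 0.85 × 45.5 + 0.15 × 26 = 42.575, or 4.4% lower in TH.
- Per observed day: a completer's rate is 45.5/39 = 1.1667 and a leaver's is 1. The means are 0.95 × 1.1667 + 0.05 = 1.1583 and 0.85 × 1.1667 + 0.15 = 1.1417, or 1.4% lower in TH.

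The daily rate removes most of this bias but not all of it.

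**The case against.** The strongest reply is that the wrong TH term could not change an analysis. A contrast acts on one response variable, and the heading, the first sentence and the endpoint lists all name rescue use. That stands as to consequence: a reader might infer that tablets would actually be tested against millimetres, and the documents do not support that. It does not remove the need for correction, since a formally tested hypothesis should be right as written and no other sentence defines its parameters.

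On truncation, the reply is that several conditions must hold together. Those who do not join must be in the analysis set, their 26-week totals must enter without imputation, and leaving or leavers' use must differ by arm. This also stands. Protocol 12.1 says generally that missing data are imputed, and Protocol 12.5 refers to the primary and secondary analyses, although the variables it then names do not include rescue use. Protocol 2 says "A subject who has signed the informed consent form (ICF) is enrolled", so an analysis of extension signers only is a possible reading, and under it the truncation largely disappears. A reader might infer from the optional consent that type I error is inflated. The table shows material inflation only at CV 0.5 with an assumed gap of 10 to 15 points between arms, and nothing in the documents supports either value. The 15% dropout in SAP 4.1.1 is an overall rate, and equal leaving gives no bias.

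It is also fair to say that a total with the missing interval imputed is as defensible as a daily rate.

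**Conclusion.** The hypothesis is wrong as written in both documents and should be corrected. That conclusion rests on the text alone and needs no assumption.

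The lack of adjustment for time observed is a secondary point. A raw total cut off at week 26 is 67% of a full one at the same daily use, but between-arm bias depends on the conditions above: 0.3% at 0% versus 1% leaving, which is negligible, and 3.4% at an assumed 5% versus 15%. These figures assume that leaving occurs at week 26 and is unrelated to use. The daily rate is therefore recommended as a cheap safeguard, not as the cure for a demonstrated bias.

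The point is confined to the last of the seven hierarchical secondary endpoints. A reader might extend it to the undefined ITT set of the extension or to the short list of imputed variables. Those matters concern the whole trial, and this finding does not establish anything about them.

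**What to change.** In Protocol 12.1.2 and SAP 4.1.3, replace the parameter definitions with wording such as: μ_DC and μ_DT are the mean rescue paracetamol use from injection through week 39 in the Cingal and TH groups respectively, where each subject's use is tablets taken divided by days covered by diary or pill count; the hypothesis is tested by the Cingal–TH contrast from the three-arm ANOVA. Use mg in place of tablets if the strength differs between the parent-trial and extension supplies.

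The cost is new wording in one section of each document and one derived variable from diaries, pill counts and dates already collected. The downside is that the measure changes from a total to a rate, with a small residual bias if daily use changes after week 26 (1.4% in the example above).

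The alternative is to keep the total through week 39, correct the TH term, and state that missing weeks 26 to 39 use is imputed. That relies on the plan's missing-at-random assumption. Choose one or the other: once the interval is imputed the total is complete, and combining imputation with an observed-day rate leaves the denominator unclear.
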